10.3.3 Recording and Follow-Up of AE and/or SAE

AE and SAE Recording

- When an AE/SAE occurs, it is the responsibility of the investigator to review all documentation (e.g., hospital progress notes, laboratory reports, and diagnostics reports) related to the event.
- The investigator will then record all relevant AE/SAE information in the eCRF.
- It is not acceptable for the investigator to send photocopies of the participant's medical records to Sponsor in lieu of completion of the AE/SAE eCRF page.
- There may be instances when copies of medical records for certain cases are requested by the sponsor. In this case, all participant identifiers, with the exception of the participant number, will be redacted on the copies of the medical records before submission to the sponsor.
- The investigator will attempt to establish a diagnosis of the event based on signs, symptoms, and/or other clinical information. Whenever possible, the diagnosis (not the individual signs/symptoms) will be documented as the AE/SAE.

Assessment of Intensity

- The investigator will make an assessment of intensity for each AE and SAE reported during the study and assign it to 1 of the following categories:
- Mild: An event that is easily tolerated by the participant, causing minimal discomfort and not interfering with everyday activities.

07 JUL 2021 Page: 77 of 90

- Moderate: An event that causes sufficient discomfort and interferes with normal everyday activities.
- Severe: An event that prevents normal everyday activities. An AE that is assessed as severe should not be confused with an SAE. Severe is a category utilized for rating the intensity of an event; and both AEs and SAEs can be assessed as severe.
- An event is defined as 'serious' when it meets at least 1 of the predefined outcomes as described in the definition of an SAE, NOT when it is rated as severe.

Assessment of Causality

- The investigator is obligated to assess the relationship between study intervention and each occurrence of each AE/SAE.
- A "reasonable possibility" of a relationship conveys that there are facts, evidence, and/or arguments to suggest a causal relationship, rather than a relationship cannot be ruled out.
- The investigator will use clinical judgment to determine the relationship.
- The investigator will also assess the relationship between each occurrence of each AE/SAE to the presence of ESRD or the hemodialysis procedure.
- Alternative causes, such as underlying disease(s), concomitant therapy, and other
 risk factors, as well as the temporal relationship of the event to study
 intervention administration will be considered and investigated.
- The investigator will also consult the Investigator's Brochure and/or Product Information, for marketed products, in his/her assessment.
- For each AE/SAE, the investigator **must** document in the medical notes that he/she has reviewed the AE/SAE and has provided an assessment of causality.
- There may be situations in which an SAE has occurred, and the investigator has minimal information to include in the initial report to the sponsor. However, it is very important that the investigator always make an assessment of causality for every event before the initial transmission of the SAE data to the sponsor.
- The investigator may change his/her opinion of causality in light of follow-up information and send an SAE follow-up report with the updated causality assessment.
- The causality assessment is one of the criteria used when determining regulatory reporting requirements.

Follow-up of AEs and SAEs

• The investigator is obligated to perform or arrange for the conduct of supplemental measurements and/or evaluations as medically indicated or as requested by the sponsor to elucidate the nature and/or causality of the AE or SAE as fully as possible. This may include additional laboratory tests or investigations, histopathological examinations, or consultation with other health

07 JUL 2021 Page: 78 of 90

care professionals.

- If a participant dies during participation in the study or during a recognized follow-up period, the investigator will provide the sponsor with a copy of any post-mortem findings including histopathology.
- New or updated information will be recorded in the originally completed CRF.
- The investigator will submit any updated SAE data to the sponsor within 24 hours of receipt of the information.

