8.3.8.1.4 Remedial Treatment for Thrombocytopenia

It is recommended that the participant receive glucocorticoid therapy to accelerate the recovery in the platelet decline (strongly recommended if platelet count < 25,000/mm³). Treatment guidelines for immune thrombocytopenia recommend dexamethasone 40 mg daily for 4 days every 2-4 weeks for 1-4 cycles; prednisolone 0.5-2 mg/kg/day for 2-4 weeks then taper; or methylprednisolone 30 mg/kg/day for 7 days (note: may require continuation with oral corticosteroids after methylprednisolone) (54).

07 JUL 2021 Page: 54 of 90

All additional platelet values, results of evaluations, and remedial treatments will be reported to the Sponsor as unscheduled laboratory visits and by updating the AESI report with all additional information, within the required timelines for follow-up information.

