8.3.8.2.2 Stopping Rule for Elevation of Hepatic Enzymes

The initial measurement(s) should be confirmed by drawing a repeat measurement at the next dialysis session (local lab- unscheduled visit), and no more than 7 days after the initial value was obtained. The repeat measurement must occur before further dosing of study intervention. Hepatic enzyme values that are not confirmed due to failure to retest or missing lab values will be presumed confirmed. In the event of confirmed laboratory results meeting the following criteria, and the event is without an alternative explanation, dosing of a participant with study intervention will be stopped permanently.

Liver Chemistry:

- 1. ALT or AST $> 8 \times ULN$, which is confirmed
- 2. ALT or AST > 5 x ULN or 5 x baseline value (if the baseline value was >ULN), which is confirmed and persists for \geq 2 weeks
- 3. ALT or AST > 3 x ULN or 3 x baseline value (if the baseline value was >ULN), which is confirmed and total bilirubin > 2 x ULN or 2 x baseline value (if the baseline value was >ULN),
- 4. ALT or AST > 3 x ULN, which is confirmed (or 3 x baseline value if the baseline value was > ULN) with the new appearance (i.e., onset coincides with the changes in hepatic enzymes) of fatigue, nausea, vomiting, right upper quadrant pain or tenderness, fever, rash, and/or concomitant eosinophilia (> ULN)

In the event that the stopping rule criteria are met during the screening period, the participant should not be randomized and will discontinue from the study.

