• To evaluate the effect of	Exploratory Efficacy Endpoints
Fesomersen on	• Incidence of the composite and event types of death due to MI, stroke, PE and SE, and stroke,

Table 2-1: Objectives and Endpoints

Objectives	Estimands/Endpoints
thromboembolic events as compared to placebo	 MI, VTE, major amputation of vascular etiology, and acute limb ischemia as assessed by the blinded CIAC Incidence of thrombosis of the arterio-venous
	grafts or fistulas, assessed by the blinded CIAC Other pre-specified Safety Endpoints
• To further evaluate the safety profile of Fesomersen as compared to placebo	• Incidence and severity of AESIs- hepatic enzyme elevation, thrombocytopenia
	• Changes in vital signs and, laboratory assessments
	• Incidence and severity of bleeding of the arterio-venous grafts or fistulas
• To further evaluate the	Other Pre-specified Pharmacodynamic Endpoints
pharmacodynamics of Fesomersen as compared to placebo	• Maximum change in PT, INR and aPTT during the main treatment period
P	• Extent and frequency of clotting on the dialysis filters & circuit
	Changes in d-dimer
	• Thrombin-antithrombin complex (TAT) and Prothrombin fragment 1 + 2 (F1.2)
Other pre-specified	
• To further investigate Fesomersen (e.g. mode-of- action-related effects, safety) and to further investigate pathomechanisms deemed relevant to cardiovascular and renal diseases and associated health problems	• Various biomarkers (e.g. diagnostic, safety, pharmacodynamic, monitoring, or potentially predictive biomarkers)
• To evaluate potential associations between genotypic information and clinical efficacy and / or pharmacodynamics effects	

It is important to note, based on the current expert assessment of the COVID-19 Public Health Emergency, it is to be expected that only a very limited number of patients (<5) will suffer from confirmed COVID-19. Besides, as ESRD patients have to go to the hospital regularly, no increase in missing data is to be expected. For this reason, no intercurrent event linked to the COVID-19 Public Health Emergency is accounted for this study. However, any premature discontinuation will be summarized, and selected analyses will be repeated by confirmed COVID-19 (Yes/No) as reported by the investigator.

3. Study Design

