6.4.2 Analysis of Secondary Safety Variable(s)

The secondary safety analysis is based on secondary endpoints incidence and severity of TEAE by treatment and overall with SAF analysis set and PA data scope.

The original terms used by investigators to report AEs via the CRFs will be coded using the Medical Dictionary for Regulatory Activities (MedDRA). The summary of all adverse events will be tabulated by the primary system organ class (SOC) and preferred term (PT) by treatment arm. A total column will be included in all safety summaries.

The version number of MedDRA used for the analyses will be stored in the clinical database. Tables and/or listings of treatment-emergent deaths, serious and significant AEs, including early withdrawals due to AEs, will also be provided.

Treatment emergent adverse events (TEAEs)

Overall study TEAEs are defined as AEs that occurred or worsened after first dosing until 20 weeks after the last study intervention dose.

Main treatment period TEAE:

The main treatment period TEAEs will be defined as those AEs that occurred after first dosing and those existing pre-dose AEs that worsened severity post-dose treatment period until 28 days after the last dose of the study drug during the main treatment period. The most conservative approach will be used to determine if the event occurs during the main treatment period.

TEAE during overall treatment period:

For the overall TEAE analysis the event which occurred during the main and extension treatment period and during the post treatment follow-up period will be considered.

All TEAEs, all TEAEs potentially related to study intervention, all TEAEs potentially related to ESRD or the hemodialysis procedure, all TESAEs, and all TESAEs potentially related to study intervention will be summarized by treatment group and by MedDRA SOC and PT terms.

TEAEs and TESAEs leading to discontinuation and AEs of special safety interest (if applicable) will be listed. The date, relative date (to start of study intervention) and phase of the study (during treatment, post-treatment) will be included.

Frequency tables, showing an overall summary of number of events, number of subjects with AEs, serious adverse events (SAEs) and adverse events of special interest (AESIs) will be given, and will include the following information.

- if AE (/SAE/AESI) occurred with causal relationship to study drug;

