6.4.4 Analysis of Other Pre-Specified Safety Variable(s)

The additional safety endpoints analysis is based on a descriptive proportion of subjects by treatment group and overall with pre-specified safety endpoints based on SAF analysis set.

- Incidence proportion of adverse events of special interests (AESIs) and severity will be summarized by treatment group and overall.
- Vital sign measures (including ECG) and the change from baseline will be summarized by treatment group and overall.

- Laboratory tests variables will be summarized by study visits, by treatment group, and overall. It will also be presented as change and percentage change from baseline over time after study intervention administration, as appropriate. In addition, the number of subjects who experience abnormalities in clinical laboratory evaluations will be summarized by treatment group and overall.
- Bleeding of the arterio-venous grafts or fistulas will be summarized by treatment group and overall. Additionally, assessment of the severity of bleeding at the dialysis access following the hemodialysis procedure will be done at specified visits. Severity of bleeding at the dialysis access will be assessed approximately 15 minutes (10 20 minutes) after removal of the dialysis needle(s) from the AV access according to the following categories (exploratory bleeding score):
 - i. "0" no access bleeding;
 - ii. "1" slow oozing;
 - iii. "2" overt bleeding

Proportion of the participants with the bleeding at the dialysis access following the hemodialysis procedure will be summarized by treatment group according to the above bleeding score categories.

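### The AESI severity summary will not show how deep a platelet fall or transaminase rise was, because the only intensity scale grades discomfort and daily function

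*Protocol*

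**What the plan says.** SAP Table 2-1 lists among the exploratory safety endpoints "Incidence and severity of AESIs- hepatic enzyme elevation, thrombocytopenia", and Protocol Table 3-1 has the same endpoint. SAP 6.4.4 gives the analysis: "Incidence proportion of adverse events of special interests (AESIs) and severity will be summarized by treatment group and overall". It names no grading scale.

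Protocol 8.3.8 defines both AESIs by laboratory thresholds alone. For platelets, the threshold is a count below 75,000/mm³ or a fall of more than 50% from baseline. For liver enzymes, it is ALT or AST above 3 x ULN, or 3 x baseline when baseline is already above ULN.

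The scale is in Protocol 10.3.3 and covers every event: "The investigator will make an assessment of intensity for each AE and SAE reported during the study". The lowest level is "Mild: An event that is easily tolerated by the participant, causing minimal discomfort and not interfering with everyday activities" and the next is "Moderate: An event that causes sufficient discomfort and interferes with normal everyday activities". The highest requires that normal daily activities are prevented. No level mentions a laboratory value, and neither document gives another scale.

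**The concern.** The endpoint asks how severe a laboratory abnormality was, and the scale supplied answers a different question. A low platelet count or a raised transaminase often has no symptom of its own. Graded as written, it stays at the lowest level however far the value moves.

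The protocol itself treats depth as what matters. It sets separate action levels for platelets and for ALT/AST, and Section 2.2.3.2 describes two thrombocytopenia cases with the parent compound as severe without reference to discomfort. Table 2-1 of the protocol lists haemorrhage, thrombocytopenia and hepatic enzyme elevation as the three potential risks of clinical significance. The primary analysis serves Phase 3 dose selection (Protocol 4.1). A table showing only mild AESIs in a dose group could therefore be taken as reassurance about depth that the grading cannot give.

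**Working it through.** No figure in the plan bears on AESI severity, so there is nothing to reproduce. The check sets the scale beside the protocol's own thresholds and then looks at what the other outputs supply.

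**1. Literal grading of events with no discomfort and no effect on activities**

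| Worst value | Protocol level passed | Grade under 10.3.3 |
|---|---|---|
| Platelets 74,000/mm³ | AESI, below 75,000 (8.3.8.1.1) | Mild |
| Platelets 49,000/mm³ | Daily monitoring, below 50,000 (8.3.8.1.3) | Mild |
| Platelets 20,000/mm³ | Below 25,000, where glucocorticoid is "strongly recommended if platelet count" is under that level (8.3.8.1.4) | Mild |
| ALT 3.1 x ULN | AESI, above 3 x ULN (8.3.8.2.1) | Mild |
| ALT 8.1 x ULN | Above 8 x ULN (8.3.8.2.2) | Mild |
| ALT 10 x ULN | Above 8 x ULN (8.3.8.2.2) | Mild |

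Several action levels collapse into one grade.

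**2. What the other planned outputs show**

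- AESI incidence by group has one entry threshold per event and carries no depth.
- Laboratory values, change and percent change by visit (SAP 6.4.4), with minimum and maximum (SAP 4.1), show one extreme per group and visit. They do not count participants beyond each level.
- Counts of participants with laboratory abnormalities (SAP 6.4.4) are not graded in the text.
- Discontinuations triggered by the platelet rule use one cut-off, 75,000/mm³ (Protocol 8.3.8.1.2), so they do not separate 74,000 from 20,000. The liver rule has several levels, but mixes them with duration, bilirubin and symptoms (8.3.8.2.2).
- Confirmatory repeats and the weekly or daily follow-up of a low count are done locally (8.3.8.1.2, 8.3.8.1.3). Additional platelet and enzyme values are reported as unscheduled laboratory visits (8.3.8.1.4, 8.3.8.2.3). The deepest values may well be among these, and the SAP does not say that by-visit summaries include them.

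**3. Platelet categories**

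Four groups cover every platelet AESI once: a fall above 50% with a count of at least 75,000; 50,000 to <75,000; 25,000 to <50,000; and <25,000/mm³. The first group can contain only participants with baseline above 2 x 75,000 = 150,000/mm³.

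**4. ALT/AST categories**

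Tiers in ULN alone would misplace participants with raised baseline, because the protocol gives alternatives such as "ALT or AST > 5 x ULN or 5 x baseline value (if the baseline value was >ULN"). With baseline at 2 x ULN, the AESI threshold is 3 x 2 = 6 x ULN and the second level is 5 x 2 = 10 x ULN. A peak of 6.5 x ULN has just met the AESI definition, yet plain tiers would put it above 5 x ULN.

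The 8 x ULN level has no baseline alternative. The 5 x baseline level passes it once baseline exceeds 8/5 = 1.6 x ULN, so the levels are better reported as counts of participants reaching each one.

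**5. How far depth categories could separate doses**

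Protocol 2.2.3.2 reports 2 severe thrombocytopenia cases in a 213-patient study and does not give the number treated. Assuming a denominator between 140 and 213, the rate is 2/213 = 0.9% to 2/140 = 1.4%. In a dose group of 72:

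- P(at least 1 case) = 1 − (1 − r)^72 = 0.493 to 0.645
- P(at least 2 cases) = 0.147 to 0.275

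Very deep events would be few, so the table would describe them without ranking doses firmly.

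**The case against.** Grading is a judgement. An investigator may decide that daily blood checks or a course of treatment do interfere with activities, so mild is the literal result and not a certain one. That stands. But if some sites depart from the written definition and others do not, the severity table becomes hard to interpret.

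Table shells sit in a separate specification that SAP Section 1 mentions and that is not available here. A laboratory grading may exist there. The supportable statement is that neither the protocol nor the SAP contains one.

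A reader might infer that the trial will be uninformative about platelet and liver safety for dose choice. The documents do not support that. AESI incidence, percent change, per-visit extremes and laboratory-triggered discontinuations are all independent of the intensity grade. Seriousness is too: Protocol 10.3.2 names blood dyscrasias among its examples. Testing is two-weekly in the main period (Protocol 8.2). AESI severity is exploratory and is nowhere named as a criterion for dose selection.

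A reader might also infer from SAP 6.4.2, which counts "those existing pre-dose AEs that worsened severity post-dose treatment period", that a pre-dose thrombocytopenia deepening without symptoms would escape the treatment-emergent tables. For platelets this is largely moot. Screening counts below 120,000/mm³ are excluded (Protocol 5.2), AESIs are reportable only after randomization, and a later threshold crossing is a new event.

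**Conclusion.** The point holds as a reporting gap of minor to moderate size. The AESI severity summary will not reflect the depth of the laboratory abnormality when the event is truly asymptomatic and the written scale is followed. Other outputs recover part of that information, but none stated in these documents counts participants by worst value, and none clearly brings in the unscheduled and local results.

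The size cannot be put as a percentage, because the share of asymptomatic AESIs is not given. The conclusion assumes that investigators apply the definitions in Protocol 10.3.3 as written and that the unseen table specification adds no laboratory grading. It affects no sample size, error rate or primary endpoint. It does not extend to the treatment-emergent definition or to the trial's overall ability to inform dose choice.

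**What to change.** In SAP 6.4.4, state that severity of the two laboratory-defined AESIs is reported by treatment group as the worst post-baseline category in the data scope, using central, unscheduled and local values recorded in the eCRF.

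- Platelets: fall above 50% with count ≥75,000; 50,000 to <75,000; 25,000 to <50,000; <25,000/mm³.
- ALT/AST: participants reaching >3, >5 and >8 x ULN, with the protocol's 3 x and 5 x baseline alternatives replacing the first two when baseline is above ULN. Add a flag for total bilirubin >2 x ULN, or 2 x baseline if baseline is above ULN.

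Add a cross-reference in Protocol 10.3.3 and keep the mild, moderate and severe scale for all other adverse events. Because SAP 6.5 says the primary analysis is already complete, apply this to the final analysis and label the table for the primary analysis (PA) data scope as supplementary.

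These are reporting categories at existing cut-offs and alter no monitoring, treatment or stopping rule. The cost is one derived variable and one extra table from data already collected.

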10.3.4 Reporting of SAEs

SAE Reporting to the sponsor via an Electronic Data Collection Tool

- The primary mechanism for reporting an SAE to the sponsor will be the electronic data collection tool.
- If the electronic system is unavailable, then the site will use the paper SAE data transmission (see next section) in order to report the event within 24 hours.
- The site will enter the SAE data into the electronic system as soon as it becomes available.
- After the study is completed at a given site, the electronic data collection tool will be taken off-line to prevent the entry of new data or changes to existing data.
- If a site receives a report of a new SAE from a study participant or receives updated data on a previously reported SAE after the electronic data collection tool has been taken off-line, then the site can report this information on a paper SAE form (see next section) or to the sponsor's Medical Monitor by telephone.
- Contacts for SAE reporting can be found in the investigator site file.

SAE Reporting to Sponsor via Paper CRF

- Email transmission of the SAE paper CRF is the preferred method to transmit this information to the Sponsor.
- In rare circumstances and if email transmission is not feasible, notification by telephone is acceptable with a copy of the SAE data collection tool sent by overnight mail or courier service.
- Initial notification via telephone does not replace the need for the investigator to complete and sign the SAE CRF pages within the designated reporting time frames.
- Contacts for SAE reporting can be found in the investigator site file.

07 JUL 2021 Page: 79 of 90

10.4 Appendix 4: Contraceptive Guidance and Collection of Pregnancy Information

Woman of Childbearing Potential (WOCBP)

A woman is considered fertile following menarche and until becoming post-menopausal unless permanently sterile (see below).

If fertility is unclear (e.g., amenorrhea in adolescents or athletes) and a menstrual cycle cannot be confirmed before first dose of study intervention, additional evaluation should be considered.

Women in the following categories are not considered WOCBP

- 1. Premenarchal
- 2. Premenopausal female with 1 of the following:
 - Documented hysterectomy
 - Documented bilateral salpingectomy
 - Documented bilateral oophorectomy

For individuals with permanent infertility due to an alternate medical cause other than the above, (e.g., mullerian agenesis, androgen insensitivity), investigator discretion should be applied to determining study entry.

Note: Documentation can come from the site personnel's: review of the participant's medical records, medical examination, or medical history interview.

- 3. Postmenopausal female
 - A postmenopausal state is defined as no menses for 12 months without an alternative medical cause.
 - A high FSH level in the postmenopausal range may be used to confirm a postmenopausal state in women not using hormonal contraception or HRT. However, in the absence of 12 months of amenorrhea, confirmation with more than one FSH measurement is required.
 - Females on HRT and whose menopausal status is in doubt will be required to use one of the non-estrogen hormonal highly effective contraception methods if they wish to continue their HRT during the study. Otherwise, they must discontinue HRT to allow confirmation of postmenopausal status before study enrollment.

Contraception Guidance:

WOCBP with their partner must agree to use a highly effective contraception method from the time signing of ICF until 20 weeks after the participant's last dose of study treatment (due to long terminal half-life and once monthly dosing).

If engaged in sexual activity with childbearing potential partner, male participants with their female partner must use highly effective contraception from the time of signing the ICF until 20 weeks after the participant's last dose of study treatment.

Highly effective contraception methods are for example:

- History of surgical sterilization (male participant or female partner)
- Female partner uses hormonal contraception or intrauterine contraception/device
- Sexual abstinence

07 JUL 2021 Page: 80 of 90

Male participants with partners that are pregnant must use condoms as contraception to ensure that the fetus is not exposed to the study intervention. Also, male participants with female partners who are breast feeding must use condoms.

Collection of Pregnancy Information:

The investigator must report to the sponsor any pregnancy occurring in a study participant, or in the study participant's partner, during the participant's participation in this study using the pregnancy reporting form. The report should be submitted within the same timelines as an SAE, although a pregnancy per se is not considered an SAE. The outcome of the pregnancy should be followed up carefully, and any outcome of the mother or child should be reported. For the pregnancy of a study participant's partner, all efforts should be made to obtain similar information on course and outcome, subject to the partner's consent.

Male participants with partners who become pregnant

- The investigator will attempt to collect pregnancy information on any male participant's female partner who becomes pregnant while the male participant is in this study. This applies only to male participants who receive study intervention.
- After obtaining the necessary signed ICF from the pregnant female partner directly, the investigator will record pregnancy information on the appropriate form and submit it to the sponsor within 24 hours of learning of the partner's pregnancy. The female partner will also be followed to determine the outcome of the pregnancy. Information on the status of the mother and child will be forwarded to the sponsor. Generally, the follow-up will be no longer than 6 to 8 weeks following the estimated delivery date. Any termination of the pregnancy will be reported regardless of fetal status (presence or absence of anomalies) or indication for the procedure.

Female participants who become pregnant

- The investigator will collect pregnancy information on any female participant who becomes pregnant while participating in this study. The initial information will be recorded on the appropriate form and submitted to the sponsor within 24 hours of learning of a participant's pregnancy.
- The participant will be followed to determine the outcome of the pregnancy. The investigator will collect follow-up information on the participant and the neonate and the information will be forwarded to the sponsor. Generally, follow-up will not be required for longer than 6 to 8 weeks beyond the estimated delivery date. Any termination of pregnancy will be reported, regardless of fetal status (presence or absence of anomalies) or indication for the procedure.
 - While pregnancy itself is not considered to be an AE or SAE, any pregnancy complication or elective termination of a pregnancy for medical reasons will be reported as an AE or SAE.
 - A spontaneous abortion (occurring at <22 weeks gestational age) or still birth (occurring at >22 weeks gestational age) is always considered to be an SAE and will be reported as such.

07 JUL 2021 Page: 81 of 90

- Any post-study pregnancy related SAE considered reasonably related to the study intervention by the investigator will be reported to the sponsor as described in Section 8.3.4. While the investigator is not obligated to actively seek this information in former study participants, he or she may learn of an SAE through spontaneous reporting.
- Any female participant who becomes pregnant while participating in the study will discontinue study intervention.

